1.5. EXPECTED BENEFITS

PUL surgery is a mini-invasive alternative to BPH standard surgery, performed under local anaesthesia in a day-care surgical unit, which need less operating time, less use of urinary catheter, and less length of stay. The procedure consists of implanting devices and does not involve resection of prostatic tissue, which should avoid some complications.

BPH standard surgery is associated with a significant amount of post-operative complications, as well as with some persistent side effects such as sexual dysfunction and urinary incontinence. Moreover, those persistent side effects may decrease urinary and sexual comfort, which strongly affect the quality of life.

As the procedure does not involve resection of prostatic tissue, we can expect less bleeding complications.

As we expect less use of urinary catheter, infectious complications should be reduced.

This procedure does not involve risk of urinary sphincter lesion so we can expect at least not worse and probably less urinary incontinence.

For men who maintain regular sexual activity, the procedure should preserve ejaculation.

For the type of patient selected in the clinical trial, we think that PUL surgery could achieve acceptable functional improvements compared to baseline and to those of standard surgery.

If our assumptions are confirmed, PUL surgery could be an efficient alternative to standard surgery, with a reduced time and amount of care and fewer complications, as well as an improvement of the overall long-term quality of life by avoiding persistent side effects.

1.6. JUSTIFICATION OF THE LOW LEVEL OF INTERVENTION

In 2017, the CNEDiMTS (HAS) performed a review of all available publications regarding Urolift device in order to assess its relevance in France in comparison with available standard of care (TURP).

The CNEDiMTS (HAS) performed a comprehensive review of the results of the LIFT study with 3 years follow-up data, of the BPH-6 Study, of an economic evaluation performed by the NICE in the UK, and of all the previously published data. At the end of this process, the experts of the CNEDiMTS (HAS) concluded that Urolift had an entire place in the therapeutic strategy of BOO treatment in France and could be used in daily practice. They assorted this statement by an ASA IV ranking corresponding to a minor improvement compared to standard treatment. They also asked the company (NEOTRACT, INC) to follow-up patients receiving Urolift in France by collecting their clinical characteristics, the number of implants used, the mid-long term functional results, and the need for any kind of retreatment.

Since then, Urolift has been sparsely used in France mainly due to the fact that the price of this single-use device is not covered by the hospitalization and that Urolift is still not reimbursed by the French Healthcare System.

In the setting of the ECOLIFT study, the Urolift device will be used following the exact recommendations of the HAS (same inclusion/exclusion criteria). The ECOLIFT protocol strictly reproduces the clinical use of Urolift without any additional clinical visit or any invasive procedure due to the research protocol as compared to French standard of care (TURP).

Additionally, the aim of our study is not to assess again its clinical effectiveness but to measure its economical value in the setting of the French Healthcare System to support the need of its reimbursement.

Finally, surgeons participating to the ECOLIFT study will have to be experienced with this procedure or to be specifically trained upfront any participation to the ECOLIFT study. Experience of at least 15 cases will be required. If the selected surgeon does not have sufficient experience, specific assistance will be provided by the company for his/her training (visit in an expert center for case observation, surgical mentoring for at least 5 cases, and 10 additional cases performed alone with possible critical review of a recorded video by an expert).

Considering that Urolift will be used in the exact setting of its recommended clinical usage (CNEDiMTS HAS recommendations) with no additional procedure compared to the standard of care, that our main objective is to perform an economic evaluation without any new clinical usage investigation and that the surgeons will have

sufficient experience before entering the study, we assume the fact that this protocol must be considered at low level of intervention with minimal risks and constraints.

2. STUDY OBJECTIVES

2.1. MAIN OBJECTIVE

To assess the incremental cost-effectiveness ratio of PUL compared with transurethral surgery 4 months after initial hospitalization.

2.2. SECONDARY OBJECTIVES

To assess the incremental cost/effectiveness ratio of PUL compared with transurethral surgery at 12 months.

The secondary objectives will be also to compare between the PUL and the transurethral procedures:

- The real cost of hospitalization related to each surgery procedure from the hospital point of view
- The overall and specific urogenital healthcare consumptions at 4 months, 1 year and 3 years following the surgical procedures;
- The BPH retreatment (including medical and surgical treatments) at 1 and 3 years after surgical procedures;
- The urinary symptoms at 4 months and 1 year after surgical procedure;
- The global quality of life, including sleep comfort at 4 months and 1 year after surgical procedures;
- The time to complete recovery and to return to normal professional activities evaluated at 1, 2, 3 and 4 months:
- The sexual side effects at 4 months and 1 year after surgical procedures;
- The complications associated with the surgical procedures at 4 months after surgical procedures.

3. STUDY OUTCOMES

3.1. PRIMARY OUTCOME

The primary endpoint will be the incremental cost per avoided complication (based on Clavien Dindo classification) of PUL compared to transurethral surgery 4 months after the surgical procedure.

3.2. SECONDARY OUTCOMES MEASURES

Secondary endpoints will be:

- The incremental cost/Qaly of PUL compared to transurethral surgery at 12 months
- The total hospital cost of each surgery procedure based on a top down micro-costing method performed during hospitalization stay
- Overall and specific urogenital healthcare consumptions at 4 months, 1 year and 3 years following the surgical procedure
 - Dispensed medications identified using the corresponding codes of the Anatomical Therapeutic Chemical (ATC) Classification;
 - o In- and out-patient visits;
 - Hospitalisation and their corresponding discharge diagnoses coded according to International Classification of Disease, 10th revision;
 - Medical procedures;
 - Nursing acts and physiotherapy;
 - Medical imageries and lab tests;
 - Transport;
 - Sick allowances;
 - At 4 months: all healthcare consumptions which are not reimbursed, but payed by the patient (e.g.: urinary incontinence products).

• BPH retreatment,

• Any dispensing of the following medications at 1 and 3 years after surgical procedure: alpha-blockers (ATC code G04CA) or 5-alpha-reductase inhibitors (ATC code G04CB);

 Hospitalization at 1 and 3 years after surgical procedure, with the main diagnosis of BPH (ICD-10 code N40) and the surgical procedure codes JGNE003, JGNE171, JGNJ001, JGFA005 JGFA009, JGFA015, JGFE023, JGFE365.

Urinary symptoms,

- Urinary incontinence evolution between inclusion and 4 months after surgical procedure (Incontinence Severity Index (ISI));
- International consultation on Incontinence questionnaire for Urinary incontinence short form (ICIQ-UI SF)
- Hospitalization with a discharge diagnosis ICD-10 code related to an urinary infection (code N41 for acute prostatitis or code N10 for acute pyelonephritis) at 1 and 3 years after surgical procedure;
- Hospitalization with a discharge diagnosis ICD-10 code related to urinary retention (R33) at 1 and 3 years after surgical procedure;
- Hospitalization with a discharge diagnosis ICD-10 code and/or medical procedure related to urethral stricture at 1 and 3 years after surgical procedure.

• Global quality of life,

- IPSS and IPSS-Q8 evolution between inclusion, 4 month, and 1 year after surgical procedure;
- O Jenkins sleep questionnaire between inclusion, 4 months, and 1 year after surgical procedure;
- EQ-5D-5L questionnaire (appendix 2) evolution between inclusion, 4 months, and 1 year after surgical procedure;

• The time to complete recovery and to return to normal professional activities

- Recovery after surgery (Quality of Recovery visual analogue score (QoR VAS)) at 1, 2, 3 and 4 months after surgical procedure;
- Time before returning to professional activities.

• Sexual side effects,

• Sexual quality of life evolution between inclusion, 4 months and 12 months after surgical procedure (IIEF15, Male Sexual Health Questionnaire for Ejaculatory Dysfunction (MSHQ-EjD).

Associated complications,

• Clavien Dindo classification of adverse events at 4 months after surgical procedure.

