1.1.2. ON THE STRATEGIES/PROCEDURES AND THE STUDY

1.1.2.1. Transurethral surgery

In France about 60.000 transurethral procedures for BOO are performed each year. However, even if bipolar and laser surgery have dramatically improved surgical outcomes in terms of length of hospital stay and post-operative complications, these procedures remain associated with a significant amount of infectious and bleeding complications, as well as with some persistent side effects such as sexual dysfunction and urinary incontinence (2, 3).

The incidence of post-operative complications has been evaluated in many RCTs comparing different surgical procedures. Clavien Dindo complications grade 2 and higher were experienced by 20 to 40% of patients depending on the surgical technique. Most of complications related with surgery are occurring within 3 months after surgery. After the first 3 months, delayed complications such as urethral strictures, bladder neck sclerosis and urinary incontinence may lead to additional surgical treatments. LUTS recurrence may also lead to restarting medical treatment or secondary surgical treatment .

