9.2. SUMMARY TABLE OF ASSESSEMENTS

Assessments carried out as part of the care (C) or specifically for research (R).

rissessments carried out as			V1	V2	V3	V4	V5
	Inclusion	Intervention	Month 1	Month 2	Month 3	Month 4	Month 12
			(+/- 7 days)	(+/- 7 days)	(+/- 7 days)	(+/- 7 days)	(+/- 14 days)
Patient information (R)	✓						
Informed consent (R)	✓						
Verification of eligibility criteria (R)	1						
Medical and surgical history (R)	1						
Drugs whether or not related to BPH (R)	1	✓	1	1	1	1	✓
Recovery after surgery (R)			✓	✓	✓	✓	
Clinical examination (C)	✓					✓	✓
Biological examination ¹ (C)	✓					✓	1
Urinary flowmetry (C)	✓					✓	✓
Urinary tract ultrasound (C)	✓						
Urine microscopic examination (C)	1	√					
Functional and quality of life questionnaires ² (R)	1					1	√
Complications and adverse effects (R)		/	1	1	1	1	✓
Cost of hospitalization (R)		√					
Health care consumptions (declared by the patient) (R)			1	1	1	1	

¹Blood sample tests: total PSA and creatinine dosage

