9.8. SNDS ASSESSMENTS

For each patient identified in the SNDS cohort, the following settings will be defined:

- Inclusion date: date of the surgical procedure completion
- **Look-back period:** 2 years preceding the inclusion date;
- **Follow-up period:** 3 years following the inclusion date.

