11.2. STATISTICAL METHODS EMPLOYED

11.2.1. GENERALITIES

Statistical analysis will be performed using SAS® software (SAS Institute, latest current version, North Carolina, USA). Qualitative and ordinal variables will be summarized by frequencies and proportions of each modality, taking into account missingness as a modality. Continuous variables will be summarized by size, number of patients with missing data, arithmetic mean, standard deviation, median, interquartile ranges and extreme values. Confidence intervals will be estimated using Normal approximation for quantitative and qualitative relevant parameters, or bootstrapping method for costs when count < 100 patients.

Standardized mean differences (*Rosenbaum*, *Rubin*, 1985) will be estimated to measure the effect size of quantitative and qualitative baseline characteristics between groups (PUL and TURP cohorts, matched patients of PUL and SNDS cohorts).

For confidence intervals, 2-sided confidence level of 95% will be used. For all tests, a 2-sided significance level of 5% will be used:

- Proportions will be compared between two independent groups using Pearson's Chi-2 test (or Fisher's exact test when expected counts are < 5)
- Means will be compared between two independent groups using Student's t-test when normal distribution is followed (or Mann-Whitney's test when normal distribution is not followed)
- Occurrence of events (retreatment, urinary symptoms) will be estimated across time using Kaplan-Meier estimator and compared between groups with logrank test.
- Adjusted comparisons between PUL and the TURP/Laser cohorts and between PUL and SNDS cohorts will be
 performed in intention-to-treat analysis using linear regression model when it involves quantitative variables,
 and using logistic regression model adjusted on potential confounders when it involves qualitative variables.

[figure not shown]
A Statistical Analysis Plan (SAP) will be developed and will be validated before the analyses.

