11.2.4. SECONDARY CRITERIA

The following analyses will be performed for each cohort, according to the matched treatment group:

- An estimation of the total hospital cost of each surgery procedure based on a top down micro-costing method performed during hospitalization stay;
- A description of the overall and specific urogenital healthcare consumptions during the 3 years of follow-up;
- A description of BPH re-treatment over the 3 years of follow-up (number of patients with a new BPH medication, number of patients hospitalized for BPH surgical procedure);
- A description of urinary symptoms (value of the IPSS, ISI, ICIQ-UI SF scores during the 1st year of follow-up and number of patients with hospitalization for urinary infection, for urinary retention, or for urethral stricture during the 3 years of follow-up);
- A description of the quality of life during the 1st year of follow-up using the IPSS-Q8 score, the Jenkins sleep questionnaire, the EQ-5D-5L questionnaire;
- A description of the recovery after surgery using the Quality of Recovery visual analogue score and the time before returning to normal professional activities;
- A description of the sexual side effects during the 1st year of follow-up using the IIEF15 and MSHQ-EjD questionnaire;
- A description of the associated complications (number and types).

[figure not shown]
A detailed analysis plan will be defined and will be validated by the steering committee of the study. Subsequent modifications must be made before the blinding is lifted on the database and will be systematically validated by the Scientific Council.

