20. APPENDICES

Appendix 1 : Haute Autorité de Santé (French National Health Authority) statement on Urolift

COMMISSION NATIONALE D'EVALUATION DES DISPOSITIFS MEDICAUX ET DES TECHNOLOGIES DE SANTE

AVIS DE LA CNEDIMTS 30 mai 2017

Faisant suite à l'examen du 16/05/2017, la CNEDIMTS a adopté le projet d'avis le 30/05/2017

CONCLUSIONS

UROLIFT, implant intra-prostatique

Demandeur : NEOTRACT Inc (Etats-Unis)
Fabricant : NEOTRACT Inc (Etats-Unis)

Les modèles et références retenus sont ceux proposés par le demandeur : UL-400-4

Indications retenues :	Traitement des symptômes du bas appareil urinaire (SBAU) liés à une hypertrophie bénigne de la prostate chez les patients intolérants à un traitement médical optimal ou en cas de contre-indication aux autres traitements chirurgicaux endoscopiques.		
Service Attendu / Rendu (SA) :	Suffisant, en raison de : - son intérêt pour traiter les symptômes du bas appareil urinaire - l'intérêt de santé publique compte tenu de la dégradation de la qualité de vie engendrée par cette pathologie.		
Comparateur(s) retenu(s):	Traitement chirurgical endoscopique de résection transurétrale de la prostate		
Amélioration du SA :	ASA de niveau IV (mineure)		
Type d'inscription :	Nom de marque		
Durée d'inscription :	5 ans		

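### Sections 3.2 and 11.2.4 define medical retreatment differently, and the section 3.2 wording counts a refill of a pre-operative prescription as an event

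*Protocol*

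**What the plan says.** Protocol section 3.2 lists BPH retreatment as a secondary outcome with a drug part and a surgical part. The drug part is "Any dispensing of the following medications at 1 and 3 years after surgical procedure", followed by the ATC classes G04CA (alpha-blockers) and G04CB (5-alpha-reductase inhibitors). It contains no new-use condition, no grace period and no reference to drugs taken before surgery.

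Section 11.2.4 describes the analysis of the same outcome over three years as the "number of patients with a new BPH medication", alongside the number hospitalised for a BPH procedure. New is not defined. The background in section 1.1.2.1 gives the clinical idea: "LUTS recurrence may also lead to restarting medical treatment or secondary surgical treatment".

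Section 11.2.1 fixes the comparison: "Occurrence of events (retreatment, urinary symptoms) will be estimated across time using Kaplan-Meier estimator and compared between groups with logrank test".

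The record of earlier drug use is already planned. The assessment table in section 9.2 has a drug row that starts at inclusion, section 9.8 sets a look-back of "2 years preceding the inclusion date" for the SNDS cohort, and sections 4.1 and 5.1.2 require the same two-year history for the two clinical cohorts.

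**The concern.** Many men who come to surgery for BPH may still hold a prescription for one of these drugs. No criterion in sections 5.1 or 5.2 excludes them, and section 8 prohibits no treatment. On the section 3.2 wording, a last refill after the operation is retreatment, although nothing has recurred and nothing has been restarted. With a time-to-event analysis that refill would be the man's event, probably soon after surgery, and a true restart a year later would add nothing.

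The outcome matters to the purpose of the study. Section 1.4 names earlier relapse of symptoms as a possible drawback of PUL, section 1.6 reports that the French health authority asked for data on any kind of retreatment, and the summary says that the results will support reimbursement. A retreatment rate that mixes refills with restarts does not answer that request cleanly.

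**Working it through.** **1. Set the rules side by side.** Section 11.2.4 can be read in two ways, because new is undefined.

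| Man | 3.2: any dispensing | 11.2.4, new = never used before | 11.2.4, new = not a continuation |
|---|---|---|---|
| No pre-operative use, starts at day 30 | event | event | event |
| Pre-operative use, one refill, then stops | event | no | no |
| Pre-operative use, stops, restarts at month 8 | event (at the first refill, if there was one) | no | event at month 8 |
| Pre-operative use, never stops | event | no | no |

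Only the first row is the same under all three readings. The third row is the restart that section 1.1.2.1 describes, and one reading of section 11.2.4 misses it.

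**2. Reproduce the plan's own figures.** The only stated figures that bear on a binary outcome are the confidence-interval half-widths in section 11.1. With 1.96 × √(p(1−p)/n):

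- n = 80: 6.57% at p = 10% and 10.96% at p = 50% (stated 7% and 11%).
- n = 400: 2.94% and 4.90% (stated 3% and 5%).

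All reproduce, and none changes with the definition. The protocol gives no retreatment rate and no rate of pre-operative drug use.

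**3. Equal carry-over (all rates assumed).** Let p be the true restart rate and r the share of the other men who only refill. Then

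observed rate = p + (1−p)r, and with equal r the difference becomes (1−r) × (true difference).

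Take p = 20% for PUL and 10% for TURP/laser. Power is for a two-sided 5% comparison of two proportions, Φ[(|Δ| − 1.96·SE₀)/SE₁], with SE₀ pooled and SE₁ unpooled. It ignores matching and is a guide to the logrank test, not a calculation of it. For r = 0 and 80 v 80, SE₀ = 0.0565 and SE₁ = 0.0559, so (0.10 − 0.1107)/0.0559 = −0.19, which gives 42%.

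| r in both groups | PUL v TURP/laser | Difference | Odds ratio | Power 80 v 80 | Power 80 v 400 |
|---|---|---|---|---|---|
| 0 | 20% v 10% | 10 points | 2.25 | 42% | 69% |
| 10% | 28% v 19% | 9 points | 1.66 | 27% | 45% |
| 20% | 36% v 28% | 8 points | 1.45 | 19% | 31% |
| 40% | 52% v 46% | 6 points | 1.27 | 11% | 16% |

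If the true rates are equal (15% v 15%), equal refilling leaves the difference at 0. It creates no false effect.

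**4. Unequal carry-over (assumed).**

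- True 20% v 10%, r = 10% PUL and 30% TURP/laser: 28% v 37%, a difference of −9 points. The sign is reversed.
- True 20% v 10%, r = 30% and 10%: 44% v 19%, a difference of +25 points.
- True 15% v 15%, r = 10% and 30%: 23.5% v 40.5%, a difference of −17 points, odds ratio 0.45.

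**The case against.** The best reply is that the detail has been deferred. Section 14.3 leaves decision rules and outcome definitions to a data management plan, and section 11.2 leaves the analysis to a statistical analysis plan. Washouts and new-user rules usually live there, and their absence from a protocol is no fault. That much stands. But the protocol does not stay silent: it states two rules that disagree, and deferral does not say which one the later plan should carry out.

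It can also be said that section 11.2.4 on its face excludes continued treatment, that section 3.2 sits under a retreatment label, and that section 3.2 names no start for the event window. All true. So the finding is a conflict between two statements, not a flawed rule that is certain to be applied, and a cluster of events just after surgery is a consequence of one reading, not something that the protocol states.

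A reader might infer that refills favour PUL by a known amount, because the indication in Appendix 1 includes men intolerant of optimal medical treatment ("chez les patients intolérants à un traitement médical optimal") and section 1.6 says that the device follows that recommendation. The documents do not carry the argument that far. The same indication has an alternative limb, a contraindication to other endoscopic surgery. The criteria in section 5.1 do not require intolerance and are the same for both clinical cohorts. Unequal drug use is still plausible: the groups are not randomised, the logrank test is unadjusted, and the matching score predicts complications, so it does not guarantee balance on these drugs. Plausible is as far as it goes.

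**Conclusion.** The two sections define the same outcome differently and must be reconciled; that rests on the text alone. Under section 3.2 as written, a refill of a pre-operative prescription is an event. Equal carry-over dilutes a true difference by the factor (1−r) and costs power. Unequal carry-over can inflate, mask or reverse it. Every restart and refill rate above is an assumption, and since the protocol reports none, neither the size nor the direction of any bias can be derived.

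Two further inferences should be resisted. The 13.6% in section 1.1.2.2 is a five-year surgical retreatment rate from one trial and is no yardstick for a drug-dispensing rule. Nor does the protocol call retreatment its main durability outcome: the drug rule is one part of one secondary outcome. The surgical part and the primary endpoint, cost per avoided complication at 4 months, are untouched. The point is worth settling before the SNDS analysis, but it does not threaten the main result.

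**What to change.** Put one definition in sections 3.2 and 11.2.4 and apply it identically in all three cohorts, using the inclusion drug record and the SNDS look-back.

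- **No pre-operative dispensing of G04CA or G04CB:** any post-operative dispensing is medical retreatment.
- **Pre-operative use:** a dispensing counts only after a prespecified dispensing-free gap, for example 90 days, with 60 and 120 days as sensitivity analyses.
- **Men who never stop:** report them as a separate category, and state how they enter the Kaplan–Meier analysis so that they do not pass silently as event-free.
- **Prior use:** show results by drug use before surgery and adjust for it.
- **Any dispensing:** keep it as a sensitivity analysis, since it is a defensible measure of continuing drug need.

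A single gap rule for everyone would be simpler, but it would lose a man with no earlier use who starts a drug soon after surgery for persistent symptoms. Section 1.4 accepts that PUL may relieve symptoms less, so that loss could favour PUL.

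The cost is a change of outcome wording and slightly more analysis; section 6 confirms that the SNDS holds dispensing dates, so no new data are needed. The gap length is arbitrary, which is why the sensitivity analyses are part of the proposal.

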1.4. RISK/BENEFIT RATIO

PUL surgery is a mini-invasive alternative to BPH standard surgery, which is intended to avoid post-operative complications and some long-term side effects, while keeping a reasonable efficiency to treat LUTS. The post-operative complications are mainly related to infections and bleeding, and are responsible of the morbidity of the BPH surgery. The persistent complications as urinary incontinence strongly affect the long-term quality of life.

Performing PUL surgery may decrease the risk of post-operative complications related with infections and bleeding. Performing PUL surgery may decrease the risk of the persistent urinary and sexual side effects and preserve quality of life.

Performing PUL surgery may be less effective than standard surgery in terms of LUTS treatment.

Performing PUL surgery may lead to earlier relapse of LUTSs compared to standard surgery.

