 - Primary diagnosis is the health problem that motivated the admission in the hospital. It is determined at
 hospital discharge. For patients hospitalized successively in several medical units, the primary diagnosis
 of the hospitalization, as well as for all medical unit primary diagnosis, are generally taken into account to
 define the occurrence of an outcome in a pharmacoepidemiology study.
 - A related diagnosis can exist only if the primary diagnosis is a care procedure with a code Z of the ICD10 classification (e.g. chemotherapy session) for a chronic or LTD disease. It indicates the pathology at the origin of the care procedure.
 - Associated diagnoses are specified mainly if they represent specific healthcare resources. They are mainly
 underlying chronic diseases. Associated diagnoses can be used to define chronic diseases but are
 generally not taken into account to define the occurrence of an outcome in a pharmacoepidemiology study
 (many being false positives for the studied outcome).

Access to SNDS is regulated and needs approval from the National Institute of Health Data (*Institut National des Données de Santé* - INDS), the committee in health data research (*Comité d'Expertise pour les Recherches, les Etudes et les Evaluations dans le domaine de la Santé* - CEREES), and the French data protection commission (*Commission Nationale de l'Informatique et des Libertés* - CNIL).

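### Surgical BPH retreatment is counted only in stays with N40 as main diagnosis, so a repeat prostate operation in a stay coded otherwise is missed and the outcome is narrower than its objective

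*Protocol*

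**What the plan says.** Protocol section 3.2 (secondary outcomes) gives BPH retreatment two parts: dispensing of two drug classes, and surgery. The surgical part is "Hospitalization at 1 and 3 years after surgical procedure, with the main diagnosis of BPH (ICD-10 code N40) and the surgical procedure codes" followed by eight codes: "JGNE003, JGNE171, JGNJ001, JGFA005 JGFA009, JGFA015, JGFE023, JGFE365". The two conditions are joined by 'and'.

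The neighbouring hospital outcomes in 3.2 are looser. Retention is "Hospitalization with a discharge diagnosis ICD-10 code related to urinary retention (R33) at 1 and 3 years after surgical procedure", with no requirement that the diagnosis be the main one. Infection is worded in the same way. Stricture is "Hospitalization with a discharge diagnosis ICD-10 code and/or medical procedure related to urethral stricture", so either element suffices.

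Section 6 explains the coding: "Primary diagnosis is the health problem that motivated the admission in the hospital". It adds that this diagnosis is fixed at discharge, and that for stays across several medical units the primary diagnosis of each unit is generally considered as well. Associated diagnoses are "generally not taken into account to define the occurrence of an outcome in a pharmacoepidemiology study".

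The objective in 2.2 is BPH retreatment, medical and surgical, at 1 and 3 years, with no limit by reason for admission. Section 11.2.4 describes the surgical count as "number of patients hospitalized for BPH surgical procedure", again without N40 as main diagnosis.

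**The concern.** The main diagnosis answers why the man came into hospital; the outcome is meant to answer whether he needed another prostate operation. These can differ. A man who relapses with acute retention or prostatitis and is re-operated in the same stay may carry R33 or N41 as main diagnosis. He has a listed operation but is not a surgical retreatment. If R33 is coded, he appears only under urinary symptoms.

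The protocol itself names retreatment as a point on which PUL may do less well: "Performing PUL surgery may lead to earlier relapse of LUTSs compared to standard surgery" (section 1.4), and section 1.1.2.2 cites 13.6% surgical retreatment over 5 years in the sham-controlled trial. Section 1.3 justifies the 3-year claims follow-up by consequences that appear late. Section 1.6 records that the health authority asked for follow-up of any kind of retreatment. With 80 PUL patients, the number of surgical retreatments will be small, so a rule that drops even a few costs information on a result meant to support a reimbursement file.

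**Working it through.** **1. Which stays count.** Apply 3.2 as written to a later stay that contains one of the eight procedure codes.

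| Main diagnosis of the stay | Surgical retreatment under 3.2? | Counted elsewhere in 3.2? |
|---|---|---|
| N40 | Yes | – |
| R33 | No | Urinary retention |
| N41 or N10 | No | Urinary infection |
| R33 at admission, recoded N40 at discharge | Yes | Retention, if R33 is still coded |
| R33 for the stay, N40 as one unit's primary diagnosis | Probably, if the practice described in section 6 is followed | Retention |
| R33, with N40 only as associated diagnosis | No | Retention |

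The fourth and fifth rows narrow the loss. The second, third and sixth show that it is not zero. Nothing in the protocol counts a listed procedure without N40.

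**2. Plan figure for scale.** The protocol gives no expected retreatment rate. The nearest stated figure is the precision in 11.1 for n = 80, which reproduces: 1.96 × √(0.10 × 0.90 / 80) = 6.6% and 1.96 × √(0.50 × 0.50 / 80) = 11.0%, against the stated 7% and 11%.

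**3. Expected PUL events at 3 years.** Input: 13.6% over 5 years (section 1.1.2.2). Assumption: even spread over time.
- 13.6% × 3/5 = 8.16%; × 80 = 6.5 events.
- If 10% of repeat operations fall in stays not meeting the N40 rule (assumption): 6.5 × 0.10 = 0.7 lost; observed rate 8.16% × 0.9 = 7.3%.
- If 30% (assumption): 6.5 × 0.30 = 2.0 lost; observed rate 8.16% × 0.7 = 5.7%.

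**4. Effect on the comparison.** Observed rate = true rate × capture, where capture is the share of repeat operations that meet the N40 rule. Illustrative true rates: 13.6% for PUL (the 5-year figure as a stand-in) and 3%, 5% or 7% in the comparator (assumption). Power is for two independent proportions, 80 v 400 (one SNDS subgroup), two-sided 5%. It approximates the planned logrank test and ignores the matching.

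Equal capture in both groups:

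| Capture | Difference in points (comparator 3 / 5 / 7%) | Power (comparator 3 / 5 / 7%) |
|---|---|---|
| 100% | 10.6 / 8.6 / 6.6 | 91.9 / 75.2 / 50.5% |
| 80% | 8.5 / 6.9 / 5.3 | 86.2 / 66.9 / 43.2% |
| 60% | 6.4 / 5.2 / 4.0 | 77.4 / 56.7 / 35.5% |

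The ratio does not move. With a 5% comparator it is 13.6/5.0 = 2.72 at full capture and 10.88/4.0 = 2.72 at 80%.

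Unequal capture, 5% comparator:
- 70% PUL, 90% comparator: 9.52% v 4.5%, difference 5.0 points, ratio 2.12, power 45.7%.
- 90% PUL, 70% comparator: 12.24% v 3.5%, difference 8.7 points, ratio 3.50, power 82.5%.

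Unequal loss can therefore move the comparison either way.

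**The case against.** The strongest defence is that requiring N40 is a deliberate choice for specificity. The outcome is BPH retreatment, so tying the operation to a BPH diagnosis is reasonable, and the same pairing of N40 with a procedure code defines the index operation for the SNDS cohort in 5.2.1. Section 6 gives a reason to avoid associated diagnoses (false positives) and describes coding practice that lets some retention stays qualify. The re-operations are also not invisible: 3.2 collects all hospitalisations and procedures, the 12-month cost per QALY includes reimbursed expenses whatever the diagnosis, and the primary 4-month endpoint does not use this definition. Section 14.3 leaves further outcome rules to a data management plan.

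Much of this stands, and it limits the point to one secondary outcome. A reader might infer that the N40 condition only removes true events; it does not, since it also screens out listed procedures done for another reason, such as a newly found cancer. What does not stand is that the matter is still open: 3.2 fixes the definition with codes, and a data management plan that follows it would implement the narrow rule. Seeing these operations in cost totals or under retention does not put them in the retreatment rate. Cancer, the clearest specificity concern, can be handled by a direct exclusion.

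**Conclusion.** The point holds in a limited form. As written, 3.2 does not count a repeat listed operation when the stay's main diagnosis is not N40, which is narrower than 2.2 and 11.2.4. The size is unknown. The 0.7-2.0 lost PUL events rest on the assumed 10-30% loss and the even spread of a 5-year rate; the corresponding fall of about 0.8 to 2.5 points in the observed rate (8.16 - 7.34 and 8.16 - 5.71) is inside the 7-point precision stated in 11.1. Equal loss reduces the event count, absolute difference and power, and leaves the ratio about unchanged.

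Two stronger readings go beyond the documents. First, that the PUL disadvantage is necessarily understated: if capture is lower in the comparator, the absolute difference can be preserved and the ratio enlarged, and nothing in the protocol says in which cohort capture is lower. Second, that the code list omits repeat PUL or implant removal: only three of the eight codes are explained (TURP, HLE and GLV, in 5.2.1), so what the other five cover cannot be judged from this document.

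**What to change.** In 3.2, define surgical retreatment as any stay after the index stay with one of the listed procedure codes, whatever the main diagnosis, excluding stays with a prostate or bladder cancer diagnosis code. Keep N40 as main diagnosis plus a listed code as a sensitivity definition, and put the same main definition into 11.2.4 and the data management plan. Settle this before retreatment counts by cohort are seen.

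The cost is a few lines of text. Hospital discharge summaries are already part of the requested SNDS extraction (14.3), and all hospitalisations and procedures are needed for the consumption outcome, so no new data are required. The downside is slightly lower specificity for BPH as the reason for the operation: an occasional listed procedure done for another non-cancer reason will count. Comparing the two definitions will show how many stays this concerns in each cohort, which is the figure the protocol now lacks.
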